## 7 Sample Size Calculation

This study plans to enroll 120 subjects plus run-in subjects (each site will enroll 2 run-in subjects). The sample size calculation is justified as follows:

The study sample size is determined by hypothesis testing for the comparison of the primary endpoint versus the performance goal (PG). The study's PG is set as 80%. The primary hypothesis test of the primary endpoint is:  $H_0: P \leq P_0$  (80%) vs.  $H_1: P > 80\%$ , where  $P$  is the actual Technical Efficacy Rate of the Neuwave Certus Microwave Ablation System. A sample size of 120 subjects is necessary to achieve at least 80% power for demonstrating that the Technical Efficacy rate of the NeuWave Certus Microwave Ablation System is  $> 80\%$  when the expected performance is 90% and a one-sided significance level of 0.025 is used with the Normal Approximation to the Binomial distribution (Z-test that uses  $S(P_0)$  to estimate the standard deviation), with adjustment for up to 10% dropout.

Each site will enroll 2 subjects first in the run-in phase. So the total sample size will be 120 subjects plus run-in subjects (each site will enroll 2 run-in subjects).

Of the 120 non run-in sample, the number of cases for either disease type is limited at up to 75% (i.e., in the 120 non run-in sample, up to 90 subjects could be NSCLC or oligometastatic lung tumor).

In addition, given the lack of available clinical data for the evaluation of the performance of the investigational product in pulmonary tumor ablation procedures, an adaptive approach will be used to re-estimate the sample size as per the "promising zone" method of Mehta and Pocock (2011) after 50% of the target enrolled subjects complete the Visit 3 Technical Efficacy Evaluation. This procedure involves evaluation of the conditional power (CP) in the interim analysis. If the CP is to fall in the pre-specified "promising zone", the sample size will

be increased to boost the CP up to the target level of 80% for the primary effectiveness endpoint, in the meanwhile, the new sample size will be subject to a predefined maximum value (200 enrolled subjects). If the CP is to fall out of the pre-specified “promising zone”, the study will maintain the originally planned sample size, i.e. 120 subjects plus run-in subjects. For details in sample size re-estimation method, please refer to Section 8.12.

## 8 Statistical Analyses

### 8.1 General Conventions

In addition to listing variables of interest, analysis methods for this study will focus on summaries using descriptive statistics appropriate to the type of variable under consideration.

- Categorical variables will be presented as frequencies and percentages.
- Continuous variables will be presented with the number of values, the number of missing, mean, standard deviation, median (Q1, Q3), minimum, and maximum values.
- For percentage calculation, the number of missing data will be not included in the denominator unless otherwise specified.

All listings, including scheduled visits and unscheduled visits, will be listed on all SAF subjects, and sorted by stage (run-in, non run-in phase), site ID, and subject ID unless otherwise specified.

All analyses will be conducted using SAS version 9.4 or higher.

### 8.2 Disposition of Study Subjects

Subject disposition will be presented for all screened subjects.

The number of subjects screened (failed, screen failure reasons, enrolled), in each analysis set, those who received ablation and those who complete and discontinue the study along with the specific reasons for discontinuation will be tabulated in total and also by site.

Identified lesion to be ablated disposition will be summarized by target lesion (yes, no) using counts in the SAF.

Listings will be provided and sorted by screening status (failed, enrolled), screening failed reason, phase (run-in, non run-in phase), site ID, subject ID, date of ablation, subject status, and date of study completion/early discontinuation.

### 8.3 Protocol Deviation

Protocol deviations will be presented for all enrolled subjects.

All protocol deviations and major protocol deviations will be tabulated by categories. Number of subjects and percentage for each category will be provided.

All protocol deviations will be listed and sorted by type (major, minor), site ID, subject ID, and deviation sequence number.

#### **8.4 Demographics and Baseline Characteristics**

Analyses will be conducted on the SAF, FAS, and run-in set.

Demographics and other baseline characteristics will be summarized using descriptive statistics. Continuous variables include age and vital signs, including weight, height, and BMI [derived as weight (kg) divided height (m^2)]. Categorical variables include age category ( $\leq$ 50 years,  $>$ 50 years), gender (male, female, for females: of childbearing potential, permanently sterilized, postmenopausal), ethnicity group, race, ECOG-PS score, smoking status, number of target lesions (identified and ablated) (1,2,3), number of identified lesion to be ablated but not ablated (0,1,2,3), number of identified lesion not to be ablated (0,1,2,3,4,5), subject target tumor diagnosis (stage IA1 NSCLC, Stage IA2 NSCLC, Oligometastatic lung tumor, other).

Listings will be provided.

#### **8.5 Medical History/ Surgical history**

Analyses will be conducted on the SAF, FAS, run-in set

Medical history/Surgical history will be summarized by each category and also by presenting number and percentage of participants by System Organ Class (SOC) and Preferred Term (PT) using MedDRA; each participant could have medical history under multiple SOC and PT, but each participant will be counted only once within each category, each SOC and PT.

Listings will be provided.

#### **8.6 Radiotherapy History**

Analyses will be conducted on the SAF, FAS, run-in set.

Radiotherapy history will be summarized by treated lesion types (primary lung tumor related, secondary lung tumor patient's original lesion related, secondary lung tumor patient's metastatic lesion related, and other).

Listings will be provided.

#### **8.7 Prior and Concomitant Medications/Procedures**

Analyses will be conducted on the SAF, FAS and run-in set.

Prior medications/procedures will be defined as medications/procedures that start prior to the date of initial ablation. Concomitant medications/procedures will be defined as medications/procedures that start on or after the date of initial ablation, or start before initial ablation but still ongoing use on the date of initial ablation.

Prior/concomitant medication/procedures will be summarized by medication category/procedure type and indication that medication/procedure taken for, respectively.

The medication categories include:

- Blood-thinning/anticoagulants
- Anti-neoplastic agents
- Steroids/Anti-inflammatory drugs/ NSAIDs
- Antibiotics
- Others

In addition, the indication categories include:

- Prophylactic
- Adverse Event
- Medical History
- Disease under investigation
- Other

Listings will be provided.

## **8.8 Lesion assessment**

Analyses will be conducted at the target tumor level on the SAF, FAS, and run-in set.

For target tumors, defined as the tumors that have been identified to be ablated and receive ablation power during the initial ablation procedure, the following tumor characteristics will be summarized:

- lung tumor type (primary lung tumor, secondary lung tumor, other), type of ground glass opacity (GGO) (pure GGO, partial GGO, pure solid tumor).
- tumor diagnosis category, location of original tumor, and any other metastatic site (for oligometastatic lung tumor only).
- number, location, and size (the size measured nearest to the ablation date will be used if size is collected more than once) of the tumor to be ablated.
- For primary and secondary tumors, biopsy results (pathology type) of the lesion to be ablated.

All identified lesions to be ablated at visit 1 will be listed on the SAF and sorted by phase (run-in, non run-in ), site ID, subject ID, target tumor indicator (target tumor [i.e. tumor identified and ablated], tumor identified but not ablated), and tumor ID, ablation date, tumor type.

For identified lesions not to be ablated, summary statistics will be provided for number, location, and size of tumors in the lung on all enrolled patients.

## **8.9 Primary Endpoint and Associated Hypotheses**

Analyses will be conducted on the FAS, PPS, and run-in set.

The primary efficacy endpoint is Technical Efficacy Rate, defined as the percentage of tumors that are completely covered by the ablation area without signs of pathological enhancement as assessed by lung enhanced CT at Visit 3 (i.e., 30 days $\pm$ 7 days after the first ablation). Each subject will have a maximum of one NSCLC tumor or a maximum of three ipsilateral oligometastatic lung tumors to be ablated, each of which will be defined as a success or failure. If the initial ablated tumor had re-ablation before Visit 3 Technical Efficacy assessment, the re-ablated tumor will be considered as a failure. The re-ablation will not change or extend the subject's follow-up schedule. Technical Efficacy Rate will be analyzed based on both the target tumor level and subject level.

The Technical Efficacy Rate is assessed by both the study physician (i.e., PI) and Independent Central Imaging Committee (IRC). Primary statistical analysis and hypothesis testing for the primary effectiveness endpoint will be based on IRC's evaluation results. For IRC evaluation, there will be at least two reviewers providing their results. If the two reviewer's results are the same, the first one's result will be used. If the two reviewer's results differ, a third reviewer will evaluate and his or her result will be used for the analysis. This analysis rule will be applied for all IRC-based endpoint.

The null and alternative hypotheses for primary analysis of the primary endpoint are as follows:

$$H_0: P \leq P_0 (80\%)$$

$$H_1: P > 80\%,$$

where P is the actual Technical Efficacy Rate using the NeuWave Certus Microwave Ablation System.

If the initial ablated tumor had re-ablation before the Visit 3 Technical Efficacy assessment, the re-ablated tumor will be considered as a failure. Other tumors with missing parameters or other early discontinuations will not have data imputation.

For multi-target-tumor subjects, his or her largest Target Tumor, determined by the maximum three dimensions of each target tumor, will be used for subject-level analysis conservatively.

The number and proportion of tumors/subjects achieving Technical Efficacy at Visit 3 will be summarized and the corresponding 95% CI based on the Normal Approximation to Binomial Distribution (Z-test that uses S(P0) to estimate the standard deviation) or Clopper-Pearson method (if the proportion is greater than 90%) will be calculated.

The success criterion of the primary effectiveness endpoint will be met if the lower limit of the two-sided 95% CI for Technical Efficacy Rate is higher than 0.8.

The following additional sensitivity analyses will be conducted for the primary effectiveness endpoint using same statistical method:

- Sensitivity analysis 1: based on the PP population at both the target tumor level and subject level.
- Sensitivity analysis 2: based on the FAS and different imputation rule for missing data of the primary effectiveness endpoint (see in Section 8.14) at both the target tumor level and subject level.

Additional analysis: based on the FAS and primary effectiveness endpoint values assessed by the investigator at the target tumor level.

Listings, including IRC assessment and PI assessment, will be provided.

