13. Patients who have received lung ablation or surgical resection therapy within 30 days prior to the ablation procedure under study and those who plan to receive lung tumor ablation or surgical resection therapy or radiation therapy on the ablated lung side before completing the primary efficacy endpoint assessment approximately 30 days after the ablation procedure.
14. Patients who received systemic therapy such as chemotherapy, targeted drug therapy, or immunotherapy within 7 days prior to the ablation procedure under study, and patients who had a systemic treatment plan such as chemotherapy, targeted drug therapy, immunotherapy, etc. before completing the primary efficacy endpoint assessment approximately 30 days after the ablation procedure.
15. Patients with uncorrectable coagulopathy based on investigator judgment.
16. Patients with a platelet count $\leq 50 \times 10^9/\text{L}$.
17. Patients who cannot discontinue antiplatelet medication (e.g., aspirin, clopidogrel, prasugrel, ticagrelor) at least **5 days** before the ablation procedure through **24 hours** post-procedure.
18. Patients who cannot discontinue anticoagulant medication (e.g., rivaroxaban, apixaban, dabigatran, edoxaban) at least **3 days** before the ablation procedure through **24 hours** post-procedure.
19. Patients who cannot discontinue warfarin before at least **5 days** before the ablation procedure of the study or have an INR > 1.5 .
20. As judged by the investigator, the patient has hypertension that cannot be effectively controlled by pharmacological treatments.
21. Severe hepatic, renal, cardiac, pulmonary or cerebral insufficiency, severe anemia, dehydration, and severe nutrition and metabolism disorders, which cannot be corrected or improved within a short term; or serious systemic infection; or severe neuromuscular diseases.
22. Expected survival less than 6 months.
23. Participation in any other interventional clinical study within 30 days before screening.
24. Physical or psychological condition which would impair study participation.
25. Patient is judged unsuitable for study participation by the investigator for any other reason.

Intra-Ablation Exclusion Criteria:

26. Before ablation probe puncture on the skin, patient is judged unsuitable for study participation due to intolerance to anesthesia.
27. Before ablation probe puncture on the skin, patient is judged unsuitable for study participation due to presenting any other condition.

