 - (4) Post-ablation: After the ablation is completed, confirm the ablation procedure is completed using CT taken approximately 10 minutes after the ablation is completed and

determine whether the ablation lesion covers the tumor. If the ablation margin is not sufficient (i.e. Did not reach at least 5mm of safety margin for oligometastatic lung tumor or at least 1cm safety margin for NSCLC), the study physician should repeat the ablation to achieve an adequate ablation margin if the situation permits.

- Record ablation procedure details, including but not limited to the following:
 - Procedure date and time
 - Mode of anesthesia
 - Guidance method used
 - Anatomic location of ablated tumor
 - Number of ablation cycles
 - Ablation power and time
- Device count: all probe types and amounts.
- Intra-ablation Screening: For patients who meet the intra ablation exclusion criteria, they will be considered an intra-ablation screening failure, and will record:
 - Informed consent date
 - Demographic information (age, race, gender, and ethnicity)
 - Reason for screening failure
- Intra-ablation Stopping Criteria and Procedure:
 - During the ablation procedure, if the investigator should stop the procedure after probe puncture but before any microwave power emission to the subject's lung tumor, due to adverse events like severe bleeding/pneumothorax, or due to any other presenting conditions, the patient will be withdrawn from the study, recording the reason, and receive a follow-up period of 30 days after the procedure from the safety evaluation perspective. If the withdrawn subject reports a SAE, the subject will be followed until resolution of the event, a stable endpoint is reached, or until the event is appropriately explained.
 - For subjects with multiple tumors identified to be ablated during screening, if not all of the identified tumors receive ablation, the reason(s) for not ablating any of the identified tumors will be recorded. The subject will not be withdrawn from study. Further treatment on the non-ablated tumors will be based on sites' SOC (i.e., not using the study devices).
- The tumors that have been identified to be ablated during screening and receive ablation power during the initial ablation procedure will be regarded as "Target Tumor(s)". Only the "Target Tumor(s)" will undergo tumor level effectiveness evaluations (i.e., Technical

Success, Technical Efficacy, and Local Tumor Progression).

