The basic tumor information(not include assessment results of investigator) will be jointly provided with the CTs to IRC, which includes enhanced CT before ablation, CT before probe insertion, CT before ablation, CT during ablation (optional) and CT after ablation, for ablation size measurement, ablation margin measurement, determination of immediate ablation results (A0, A1, A2), and determination of Technical Success Rate, A0 Ablation Rate.

2) Visit 2B

The following data will be collected after ablation till discharge:

- ECOG performance status score at day 1 after the ablation.
- Pain assessment: using the Numeric Pain Rating Scale (NPRS) at day 1 and day 3 after the ablation, this can be done by phone as needed.
- As clinically necessary, the study doctor can schedule a lung X-ray and/or lung CT scan as needed as an optional imaging test (e.g. at 1-3 days post-procedure) for a patient to assess the occurrence of post-ablation lung complications.
- Length of stay (LOS): the time from ablation completion to discharge is recorded.
- Relevant concomitant medication: including blood thinning/anticoagulants, antineoplastic agents such as chemotherapy/ targeted therapy/ immunotherapy, steroids, anti-inflammatories, NSAIDs, antibiotics and medications used to treat relevant medical history and adverse events.
- Concomitant procedure: the name, time, site and purpose of the concomitant operation (including but not limited to puncture, radiotherapy, ablation therapy and surgical resection).
- All AEs and SAEs.

NOTE: Between post-ablation and Visit 3, if the investigator considers it in the best interest of the patient to restart systemic therapy before completing the primary efficacy endpoint assessment approximately 30 days after the initial ablation, the investigator should contact the Sponsor medical monitor for discussion.

3) Visit 3

One month following the ablation procedure (30 days \pm 7 days post procedure), subjects will return to the study site for the following evaluations:

- ECOG performance status score.

- Pain assessment: using numeric pain rating scale, this can be done by phone as needed.
- Quality of Life assessments: the QOL questionnaires include the EORTC QLQ-C30 and the lung-specific QLQ-LC13.
- Enhanced CT scan of the lung.
- Document the investigator's determination of Technical Efficacy evaluation.
- Submit the CT images to the IRC for determination of Technical Efficacy evaluation.

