8.2. Calculation of Sample Size

8.2.1. Total Sample Size

It plans to enroll 120 subjects plus run-in subjects (each site will enroll 2 run-in subjects) in this clinical study. The sample size calculation is justified as follows:

The study sample size is determined by hypothesis testing for the comparison of the primary endpoint versus the performance goal (PG). PG is determined based on the results of the meta-analysis on the existing literature of similar techniques. The Technical Efficacy rate at 1 month after microwave ablation was extracted from existing literature, and then the point estimate and corresponding 95% confidence interval were estimated by meta-analysis using random effects. The meta-analysis results showed that, prior studies based on a variety of hypotheses have a mean Technical Efficacy rate of 87% (95%CI 79%-92%) at 1 month. Considering that PG is the minimum threshold of the acceptable performance, new product-related study learning curve, clinically significant Technical Efficacy rate, and lower limit of the above 95% confidence interval, the PG of the study is set as 80%.

The Technical Efficacy hypothesis test of the primary endpoint is: $H_0: P \leq P_0$ (80%) vs. $H_1: P > 80\%$, where P is the actual Technical Efficacy rate of the NeuWave Certus Microwave Ablation System. A sample size of 120 subjects is necessary to achieve at least 80% power for demonstrating that the Technical Efficacy rate of the NeuWave Certus Microwave Ablation System is $> 80\%$ when the expected performance is 90% and a one-sided significance level of 0.025 is used with the Normal Approximation to the Binomial distribution (Z-test that uses $S(P_0)$ to estimate the standard deviation), with adjustment for up to 10% dropout. Besides, each site will enroll 2 subjects first in the run-in phase. So the total sample size will be 120 subjects plus run-in subjects (each site will enroll 2 run-in subjects).

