8.2.3. Significance Level and Power of Clinical Trial

In this study, the statistical power is set as 80% for the sample size calculation of primary effectiveness endpoint test, and the significance level of hypothesis test is set as one-sided 0.025.

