8.4. Criteria and Reason for Terminating the Trial Based on the Statistical Results

There is no planned termination of the trial due to statistical reasons.

8.5. Statistical Method of All Data, together with the Handling Method of Missing, Unused and Error Data (including Termination and Withdrawal Halfway) and Unreasonable Data

All effectiveness endpoint analyses will be performed only on subjects undergoing ablation with the NeuWave Microwave Ablation System and observed data will be analyzed.

1) In the primary analysis of the primary effectiveness endpoint:

- A new subject will be recruited to replace any subject who discontinues the ablation procedure after the ablation probe punctures the skin and before the microwave energy is released.
- If an initial ablated tumor had re-ablation before the Visit 3 Technical Efficacy assessment, the re-ablated tumor will be considered as failure.
- Other subjects with missing parameters or other early discontinuations will not have data imputation.

2) A sensitivity analyses will also be performed for the primary effectiveness endpoint after missing data are imputed according to the following methods:

- A new subject will be recruited to replace any subject who discontinues the ablation procedure after the ablation needle punctures the skin and before the microwave energy is released.
- If an initial ablated tumor had re-ablation before the Visit 3 Technical Efficacy assessment, the re-ablated tumor will be considered as failure.
- As a conservative surrogate endpoint, if the subject does not have Visit 3, then chest enhanced

CT at Visit 4 will be sent to the IRC for local tumor progression assessment, and if local tumor progression occurs, the primary effectiveness endpoint at Visit 3 will be imputed as a failure. If there is no local tumor progression at Visit 4, the primary effectiveness endpoint at Visit 3 will be imputed as successful. If a subject does not have both Visit 3 and Visit 4, the subject will be excluded from the analysis of the primary effectiveness endpoint.

For secondary endpoint missing value, there will be no imputation. The handling methods for missing values and outliers are detailed in the Statistical Analysis Plan (SAP).

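### Re-ablation is the only treatment before Visit 3 that is scored as a Technical Efficacy failure; an irradiated target tumour is scored as its CT reads, and a resected one probably leaves the denominator

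*SAP*

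**What the plan says.** **Endpoint.** Technical Efficacy is judged for each target tumour on the enhanced CT at Visit 3 (30 ± 7 days). Two things are required: full coverage by the ablation zone and no pathological enhancement (SAP 1.3.1 and 8.9). The primary test uses the IRC reading on the FAS.

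**Treatment before the scan.** SAP 8.9: "If the initial ablated tumor had re-ablation before Visit 3 Technical Efficacy assessment, the re-ablated tumor will be considered as a failure". SAP 8.14 and protocol 7.2.3 (Visit 3 note), 8.1 and 8.5 repeat this rule. None of them mentions radiotherapy, resection or systemic therapy.

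**Missing results.** Protocol 8.5, for the primary analysis: "Other subjects with missing parameters or other early discontinuations will not have data imputation". SAP 8.9 says the same of tumours. In sensitivity analysis 2 (SAP 8.14), a subject without Visit 3 is scored from Visit 4: local progression is a failure and its absence a success.

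**Entry criteria.** Protocol 7.1.5, exclusion 13, bars "those who plan to receive lung tumor ablation or surgical resection therapy or radiation therapy on the ablated lung side" before the primary assessment. Exclusion 14 does the same for planned systemic treatment.

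**After entry.** The Visit 2B note in protocol 7.2.3 tells the site to contact the sponsor's medical monitor "if the investigator considers it in the best interest of the patient to restart systemic therapy before completing the primary efficacy endpoint assessment". It states no consequence for the endpoint.

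**Recording.** Concomitant procedures, including radiotherapy and resection, are recorded at Visits 2B and 3 with name, time, site and purpose, as are antineoplastic drugs (protocol 7.2.3). SAP 8.7 only summarises and lists them.

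**The concern.** Exclusions 13 and 14 run until the primary assessment is complete, so the sponsor evidently regards these treatments as able to disturb the 30-day endpoint. They act on plans at entry, however, not on what happens afterwards. The re-ablation rule implies that a target tumour needing more local treatment before Visit 3 was not adequately ablated. If a site acts on the same judgement with radiotherapy or surgery, the plan gives a different score. The result then depends partly on the modality chosen.

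The trial has one arm and is decided against a fixed 80% goal, so no control group absorbs such scoring. A masked or dropped ablation failure moves the rate upward.

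**Working it through.** **Inputs.** "the PG of the study is set as 80"% (protocol 8.2.1). Expected rate 90%. "the significance level of hypothesis test is set as one-sided 0.025" and "the statistical power is set as 80% for the sample size calculation of primary effectiveness endpoint test" (protocol 8.2.3). Dropout at Visit 3 is 10% (protocol 8.2.4). The test is a z-test with the standard deviation taken at P0 (SAP 8.9), and evaluable n is 108 (SAP 8.12.1).

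**1. The plan's own figure.** n = [(1.960·√(0.8·0.2) + 0.842·√(0.9·0.1)) / 0.10]² = 107.43, so 108; 108/0.90 = 120 enrolled. The stated size reproduces. Approximate power is 80.3%. The success rule works out as at least 95/108, with exact one-sided error 2.1% and exact power 81.0%. The gap is not a sample size error.

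**2. How each event is scored as the plan stands.**

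| Event on a target tumour before the Visit 3 CT | Primary analysis (FAS) | Sensitivity analysis 2 |
|---|---|---|
| Re-ablation | Failure | Failure |
| Radiotherapy | As the CT reads | As the CT reads |
| Resection | Probably unreadable: missing, out of the denominator | If Visit 3 is missing and Visit 4 shows no local progression: success |
| Restarted systemic therapy | As the CT reads | As the CT reads |

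**3. The boundary.** z = (x/n − 0.80)/√(0.16/n); success needs z > 1.96. All rates here are below 90%, so the SAP's switch to Clopper-Pearson does not apply. Suppose the initial ablation alone gave 94/108, and one of the 14 failures was treated again before the scan.

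| Handling of that tumour | Result | z | Lower 95% limit | Outcome |
|---|---|---|---|---|
| Scored as failure | 94/108 | 1.828 | 0.795 | Fails |
| Irradiated, reads clean | 95/108 | 2.069 | 0.804 | Passes |
| Resected, dropped as missing | 94/107 | 2.030 | 0.803 | Passes |
| Resected, imputed success in sensitivity analysis 2 | 95/108 | 2.069 | 0.804 | Passes |

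**4. Error rate for assumed frequencies.** The documents give no frequency, so the share s of tumours affected is an assumption. Take a true ablation-only rate of 0.80 and exact binomial probabilities.

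| s | Every affected tumour is a failure that reads clean (rate 0.80 + s) | Every affected tumour is a failure that drops out | Affected tumours are a random sample, all read clean (rate 0.80 + 0.2s) |
|---|---|---|---|
| 0 | 2.1% | 2.1% | 2.1% |
| 1% | 3.7% | 3.7% | 2.4% |
| 2% | 6.3% | 6.2% | 2.7% |
| 3% | 10.3% | 5.9% | 3.0% |
| 5% | 23.8% | 15.4% | 3.7% |

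The first two columns of results are worst cases. The drop-out column uses whole-number denominators (107, 106, 105, 103) and cut-offs (94, 93, 93, 91), so it is not monotone.

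**5. Power under a failure rule.** If affected tumours are ablation failures anyway, they are already in the expected 10% and planned power is unchanged. If treatment is unrelated to outcome, the rate becomes 0.9(1 − s). For s = 1%, 2% and 3% that is 0.891, 0.882 and 0.873, with exact power 71%, 60% and 49%.

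**The case against.** The case for leaving the text alone has several parts.

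- *Scored as read is not scored as success.* A reader might infer that every irradiated or drug-treated tumour becomes a success or drops out. The documents do not support that: a tumour that still enhances, or is not covered, already fails. Coverage is a separate requirement, and nothing shows that radiotherapy or chemotherapy would supply missing coverage. This stands, and limits the radiotherapy route to scans that meet both conditions.
- *Systemic therapy.* A reader might infer upward bias here too, because this is the one route that the protocol foresees. But the Visit 2B note speaks of the patient's best interest, not of an inadequate ablation, and upward bias is not shown. This stands.
- *Treatment of other tumours.* The protocol 7.2.3 sentence beginning "Further treatment on the non-ablated tumors will be based on" might be read as opening the target tumour to uncontrolled treatment. It concerns tumours that did not receive ablation power, which are not target tumours and do not enter the endpoint. This stands.
- *Existing limits.* Planned treatment is excluded at entry, and the per-protocol set can remove major deviations. These narrow the gap. However, the per-protocol analysis is only a sensitivity analysis and names none of these treatments. Removing a masked failure also does not count it as one.
- *The boundary example.* Any cut-off flips on one case, so it shows sensitivity, not bias. Also, 108 counts evaluable subjects. With up to three metastases per subject the tumour-level denominator may be larger, and the subject-level analysis uses only the largest target tumour. All of this stands.

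**Conclusion.** The point holds for further local treatment of a target tumour. Followed as written, the plan scores a re-ablated tumour as a failure, an irradiated one by its scan, and a resected one probably not at all, or as a success in sensitivity analysis 2. This is a stated rule that can give a biased answer, not just a missing detail.

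Its practical size is uncertain and probably small. No passage anticipates early radiotherapy or resection of a target tumour, or gives a frequency. With 1% to 3% affected, the false-success probability rises from 2.1% to between 3.7% and 10.3%, if every affected tumour is an ablation failure that reads clean. If affected tumours are a random sample, it reaches only 2.4% to 3.0%. One tumour matters only when the result is near 94 or 95 of 108. That a resected tumour is unreadable is an inference; the documents do not say so.

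For restarted systemic therapy the supported conclusion is narrower: the plan has no analysis showing whether the result depends on it.

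**What to change.** In SAP 8.9 and 8.14 and protocol 8.1 and 8.5, extend the existing rule along these lines:

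*A target tumour that receives any further local tumour treatment directed at it (re-ablation, resection, or radiotherapy whose field includes it) after the initial ablation and before the Visit 3 CT is scored as a Technical Efficacy failure, in the primary analysis and in sensitivity analysis 2.*

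Where no Visit 3 CT is done, the rule needs a cut-off date, for example the close of the Visit 3 window at day 37 (30 + 7). The interim rate should be scored in the same way.

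For systemic anticancer therapy restarted in the same interval, keep the IRC reading in the primary analysis and add one FAS sensitivity analysis that scores those tumours as failures. Do not class the restart automatically as a major deviation, since protocol 7.2.3 provides a discussion route for it.

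The cost is SAP and protocol wording plus one sensitivity row, ideally settled before any summary of the primary endpoint is seen. No new data and no change to patient care are needed. The reported rate may fall slightly. Power falls only to the extent that tumours treated again would otherwise have been successes.
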